6.7 End of Treatment

At the EoT for each individual participant, further therapeutic options with drugs other than regorafenib and/or nivolumab are at the discretion of the Investigator.

Clinical Study Protocol Global Amendment 1 BAY 73-4506/ 21136

27 JAN 2021

Page 61 of 135

An EoT visit will be performed within 14 days after permanent discontinuation of study treatment. Note: If the study treatment was permanently discontinued after dose interruption of more than 28 days (including drug holiday for regorafenib), the active FU visit should also occur within 14 days of discontinuation. If the EoT and active FU visits will be scheduled at the same time, the visits can be combined.

7. Discontinuation of Study Intervention and Participant Discontinuation/Withdrawal

General procedures

Discontinuation of one study drug does not constitute withdrawal from study treatment period. Permanent discontinuation of both study drugs (regorafenib and nivolumab) constitutes withdrawal from treatment period of the study. Withdrawal from treatment period (all study drugs are discontinued) does not constitute withdrawal from the study. Patients who withdraw from study treatment period for any reason should complete the active safety FU visit and should be encouraged to remain on the study for FU of primary, secondary and other objectives (i.e. continue in the active FU and long-term FU periods). Patients are expected to participate in the FU unless they explicitly object. Withdrawal of consent to treatment should be documented in the patient's medical record. If the patient does not wish to be followed up further, this additional consent withdrawal for FU must also be documented.

The criteria for withdrawal from the study are listed in Section 7.2, and the criteria for permanent discontinuation of each study drug are listed in Section 6.6.1 for regorafenib and in Section 6.6.2 for nivolumab.

In all cases, the reason for withdrawal must be recorded in the patient's medical records and in the eCRF. For patients who withdraw consent from study, no further study related procedures will be allowed. The patient will not suffer any disadvantage as a result.

If the existing local governance (for example, Health Authorities or Ethics Committees) prohibits patients who withdraw consent from study drug treatment to continue into FU, additional consent processes should be implemented to invite patients to participate in the FU.

All patients who discontinue due to AEs should be followed up until they recover or stabilize, and the subsequent outcome is recorded. If any participant dies during treatment, or within 30 d + 7 d after the last dose of regorafenib if a patient was on regorafenib monotherapy or within 100 d + 14 d after the last dose of regorafenib/nivolumab combination treatment or nivolumab monotherapy, the investigator or his/her designated associate(s) will inform the Sponsor and the cause of death should be recorded in detail within 24 hr of awareness on a Serious AE (SAE) Form and transmitted to the Sponsor.

7.1 Discontinuation of Study Intervention

Withdrawal from study treatment period

Patients **MUST** be withdrawn from both, regorafenib and nivolumab, if any of the following occurs:

- At their own request. At any time during the study and without giving reasons, a patient may decline to participate further. The patient will not suffer any disadvantage as a result.
- If, in the investigator's opinion, continuation of the study treatment would be harmful to the patient's well-being.
- Confirmed PD as per iRECIST or iRANO criteria; however, treatment may be continued provided that the patient derives ongoing clinical benefit as determined by the treating physician (Participants who complete 24 infusions of nivolumab [after approximately 2 years of treatment] need to discontinue nivolumab treatment. Regorafenib monotherapy treatment can be continued beyond 2 years until discontinuation criteria are met).
- Clinical progression (every effort should be made to obtain radiological confirmation of PD during active FU). Note: In cases where radiographic evaluation is not possible, clinical progression may be used. Clinical progression is based on the judgment of the investigator (e.g., defined as worsening of the ECOG PS ≥3 or symptomatic deterioration including increase in liver function tests).
- The development of a second primary malignancy that requires a different treatment.
- Development of any intercurrent illness or situation which may, in the judgment of the investigator, affect assessments of clinical status and study endpoints to a relevant degree.
- Severe allergic reactions, such as exfoliate erythroderma, anaphylaxis, or vascular collapse.
- Start of subsequent systemic anti-cancer treatment.
- Substantial non-compliance with the requirements of the study.
- If all study drugs (regorafenib and nivolumab) have to be permanently discontinued. Requirements for discontinuation of individual study drugs are described in Section 6.6.1 for regorafenib and in Section 6.6.2 for nivolumab.
- Use of illicit drugs or other substances that may, in the opinion of the investigator or their designated associate(s), have a reasonable chance of contributing to toxicity or otherwise confound the results.
- Pregnancy
- Participant lost to FU
- Death
- Withdrawal of regorafenib only:
 - Patients who halt therapy for more than 28 consecutive days including the 1 week drug holiday. However, continuation of regorafenib may be considered if, in the investigator's opinion, the patient may continue to benefit from the regorafenib treatment, and after consultation with sponsor.
 - Unacceptable toxicity, i.e., event requiring permanent discontinuation of regorafenib according to dose modification guidance in Section 6.6.

• Withdrawal of nivolumab only:

- Patients who experience a delay of > 10 weeks to receive the subsequent nivolumab infusion due to treatment related toxicity (see exceptions in Section 6.6.1)
 - Dosing delays to allow for prolonged steroid tapers to manage drug-related adverse events are allowed.
 - Dosing delays lasting > 10 weeks from the previous dose that occur for non-drug-related reasons may be allowed if approved by the Medical Monitor (or designee).
- Patients who complete 24 infusions of nivolumab (after approximately 2 years of treatment)
- Unacceptable toxicity, i.e. event requiring permanent discontinuation of nivolumab according to dose modification guidance in Section 6.6.1.

Withdrawal from active FU

Participants *must* be withdrawn from active FU if any of the following occurs:

- At their own request. At any time during the study and without giving reasons, a participant may decline to participate further. The participant will not suffer any disadvantage as a result.
- Radiologically confirmed PD per iRECIST or iRANO (Participants who discontinue study intervention due to confirmed radiological PD per iRECIST or iRANO will terminate the active FU period after the safety FU visits are completed
- Start of subsequent systemic anti-cancer treatment after the safety FU visits are completed
- Development of a second primary malignancy that requires a different treatment after the safety FU visits are completed
- Substantial non-compliance with the requirements of the study
- Withdrawal of consent to active FU visits
- If, in the investigator's opinion, continuation of the active FU visits would be harmful to the participant's well-being
- Participants lost to FU
- Death

Withdrawal from long-term FU

Participants *must* be withdrawn from long-term FU if any of the following occurs:

- Withdrawal of consent to long-term FU
- Participants lost to FU
- Death

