27 JAN 2021

When the two study drugs are administered on the same day, regorafenib is to be taken first orally followed by nivolumab infusion.

Regorafenib should be taken within 2 hr after a light meal with approximately 240 mL (8 fluid ounces) of water, preferably in the morning. A light meal contains less than 600 calories and less than 30% fat. If necessary, the study drug may be taken at different times of the day, but there should be consistency with respect to dosing intervals (the recommendation is to have at least a 20 hr interval between doses). Tablets should not be chewed. If a dose of regorafenib is missed, the missed dose should not be made up for (vomited tablets cannot be made up), and the next dose should be taken at the regular time. The subsequent dose of regorafenib should not be doubled. The investigator should be informed if the dose of regorafenib taken exceeded the scheduled dose.

On days of pre-dose PK all blood samples will be collected at the clinic prior to the morning dose of regorafenib. When participants are dosed at the site, they will receive regorafenib directly from the Investigator or designee.

Participants will continue treatment until any treatment discontinuation criteria apply as specified in Section 7.1.

Treatment with individual drugs (regorafenib or nivolumab) may continue on schedule even if the other drug is interrupted or permanently discontinued due to toxicity.

Participants who complete 24 infusions of nivolumab (after approximately 2 years of treatment) need to discontinue nivolumab treatment. Regorafenib treatment can be continued until clinical or radiological disease progression or unacceptable toxicity.

Treatment beyond radiological progression is possible. See Section 8.1 for additional details. In order to continue treatment after initial documentation of disease progression as per RECIST 1.1 or RANO, participant must be re-consented. Re-consent also covers a potential treatment continuation with regorafenib after confirmed radiological progression (according to iRECIST or iRANO).

Page 46 of 135

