27 JAN 2021

substituted for dedicated diagnostic contrast enhanced CT scans for anatomically based RECIST 1.1 measurements. However, if a site can document that the CT performed as part of a PET/CT is of identical diagnostic quality to a diagnostic CT (with IV and oral contrast) then the CT portion of the PET/CT can be used for response assessments.

NOTE: Lesions selected as target (measurable) lesions per RECIST 1.1 should not be biopsied. Additional guidance will be provided to the site on decisions about performing biopsies on potential target lesions when only one potential target lesion exists at baseline.

For treatment beyond RECIST 1.1 progression:

For participants who show evidence of PD by RECIST 1.1, the Investigator may decide to continue a participant on study treatment using the iRECIST guidelines (Section 10.6.2) if the participant signs a new consent for continuation of treatment beyond initial documentation of disease progression and if the following features are fulfilled:

- No worsening of performance status has occurred
- No clinically relevant increases in disease-related symptoms
- No requirement for intensified management of disease-related symptoms exists
- Absence of tumor progression at critical anatomical sites that cannot be managed by protocol-allowed medical interventions

For participants who continue treatment beyond unconfirmed progressive disease (iUPD), the next imaging assessment should be performed ≥ 4 weeks and no longer than 8 weeks later. Participants should discontinue study treatment upon confirmed progression per iRECIST (iCPD). During the treatment phase, if immune complete response (iCR), immune partial response (iPR) or immune stable disease (iSD) is determined following iUPD, imaging assessments should continue as originally planned (8 weeks (\pm 7 days) through Cycle 8 (or until treatment discontinuation, if treatment discontinuation occurs before) and every 12 weeks (\pm 14 days) thereafter). During active FU, tumor assessments should also be performed ≥ 4 weeks and no longer than 8 weeks later following any determination of iUPD until determination of iCR, iPR, iSD or until iCPD occurs.

NOTE: If a participant has iCPD, but the participant is achieving a clinically meaningful benefit, an exception to continue treatment and tumor assessments until clinical disease progression may be considered following consultation with the sponsor.

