Tumor response assessments for participants with GBM/AA:

The primary endpoint for efficacy assessment is ORR measured by RANO (Section 10.6.3) as determined by local assessment. ORR measured by iRANO (Section 10.6.4) will also be included as an exploratory endpoint. Tumor response using RANO criteria will continue until initial disease progression is detected. Both CR and PR responses should be confirmed ≥ 4 weeks later. If PR or CR is not confirmed, response will be considered only SD. If PD occurs beyond 6 months after initiation of treatment, the participant should be discontinued from treatment. For any participant deemed clinically unstable (provided that their decline is attributable to the disease and not comorbid events or changes in medication), the investigator should discontinue the participant from study treatment at site-assessed first radiologic evidence of PD without need for repeat tumor imaging for confirmation of study treatment. For

these participants, the date of progression is the date the patient developed substantial neurological decline attributable to their underlying tumor.

For treatment beyond initial RANO progression:

When a participant has an initial unconfirmed PD by RANO that is within the first 6 months of starting treatment, the investigator may consider treating past this unconfirmed PD using iRANO criteria (Section 10.6.4) if the participant is clinically stable according to the following criteria:

- No decline in ECOG PS
- No clinically relevant increase in symptoms related to the participant's cancer
- No requirement for intensified management of disease related symptoms, including increased analgesia, radiation, or other palliative care

If it is decided that the participant may continue treatment, the participant must be reconsented for continuation of treatment beyond initial RANO-based unconfirmed disease progression.

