- The target lesion sum of diameters (initial target lesions) is not above the initial PD threshold.

The response is classified as iSD or iPR (depending on the sum of diameters of the target lesions), or iCR if all lesions resolve. In this case, the initial iUPD is considered to be pseudo-progression, and the level of suspicion for progression is "reset". This means that the next visit that shows radiographic progression, whenever it occurs, is again classified as iUPD by iRECIST, and the confirmation process is repeated before a response of iCPD can be assigned.

Management Following the Confirmatory Imaging

If repeat imaging does not confirm PD per iRECIST, as assessed by the Investigator, and the participant continues to be clinically stable, study treatment may continue and follow the regular imaging schedule. If PD is confirmed (iCPD) via iRECIST, participants will be discontinued from study treatment.

NOTE: If a participant has iCPD as defined above, but the participant is achieving a clinically meaningful benefit, an exception to continue study treatment may be considered following consultation with the Sponsor. In this case, if study treatment is continued, tumor imaging should continue to be performed following the intervals as outlined in this protocol (See SoA Table 1–2)

Detection of Progression at Visits after Pseudo-progression Resolves

After resolution of pseudo-progression (i.e., achievement of iSD/iPR/iCR), iUPD is indicated by any of the following events:

Target lesions

• Sum of diameters reaches the PD threshold (≥20% and ≥5 mm increase from nadir) either for the first time, or after resolution of previous pseudo-progression. The nadir is always the smallest sum of diameters seen during the entire trial, either before or after an instance of pseudo-progression.

Non-target lesions

- If non-target lesions have never shown unequivocal progression, their doing so for the first time results in iUPD.
- If non-target lesions have shown previous unequivocal progression, and this progression has not resolved, iUPD results from any significant further growth of non-target lesions, taken as a whole.

New lesions

- New lesions appear for the first time
- Additional new lesions appear
- Previously identified new target lesions show an increase of ≥5 mm in the new lesion sum of diameters, from the nadir value of that sum
- Previously identified non-target lesions show any significant growth

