If any of the events above occur, the overall response for that visit is iUPD, and the iUPD evaluation process (see Assessment at the Confirmatory Imaging above) is repeated. Progression must be confirmed before iCPD can occur.

The decision process is identical to the iUPD confirmation process for the initial PD, with one exception: if new lesions occurred at a prior instance of iUPD, and at the confirmatory imaging the burden of new lesions has increased from its smallest value (for new target lesions, the sum of diameters is \geq 5 mm increased from its nadir), then iUPD cannot resolve to iSD or iPR. It will remain iUPD until either a decrease in the new lesion burden allows resolution to iSD or iPR, or until a confirmatory factor causes iCPD.

Page 108 of 135

Additional details about iRECIST are provided in the iRECIST publication (Seymour et al. 2017).

Tumor Assessment	Clinica	lly Stable	Clinically Unstable		
	Imaging	Treatment	Imaging	Treatment	
1 st radiologic evidence of PD by RECIST 1.1	Repeat imaging at 4 to 8 weeks to confirm PD	May continue study treatment at the Investigator's discretion while awaiting confirmatory tumor imaging by iRECIST.	Repeat imaging at 4 to 8 weeks to confirm PD per physician discretion only	Discontinue treatment	
Repeat tumor imaging confirms PD (iCPD) by iRECIST at the local site	No additional imaging required	Discontinue treatment (exception is possible upon consultation with Sponsor)	No additional imaging required	N/A	
Repeat tumor imaging shows iUPD by iRECIST per Investigator assessment	Repeat imaging at 4 to 8 weeks to confirm PD. May occur at next regularly scheduled imaging visit.	Continue study treatment at the Investigator's discretion.	Repeat imaging at 4 to 8 weeks to confirm PD per Investigator's discretion only.	Discontinue treatment	
Repeat tumor imaging shows iSD, iPR, or iCR by iRECIST per Investigator assessment.	Continue regularly scheduled imaging assessments	Continue study treatment at the local site Investigator's discretion	Continue regularly scheduled imaging assessments	May restart study treatment if condition has improved and/or clinically stable per Investigator's discretion. Next tumor image should occur every 8 weeks (±7 d) according to the imaging schedule through Cycle 8 (or until treatment discontinuation, if treatment discontinuation occurs before) and 12 weeks (±14 d) thereafter	

Table 10–4 Imaging and Treatment after First Radiologic Evidence of PD

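### The protocol contradicts itself on whether treatment may continue after confirmed progression without consulting the sponsor and whether GBM/AA has any exception; the described re-consent names regorafenib only

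*Protocol*

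**What the plan says.** Protocol Section 7.1 states that patients must "be withdrawn from both, regorafenib and nivolumab, if any of the following occurs". One item on that list is confirmed PD by iRECIST or iRANO. The same item then gives an exception: "treatment may be continued provided that the patient derives ongoing clinical benefit as determined by the treating physician". Its parenthesis recalls the 24-infusion limit on nivolumab and adds nothing about the sponsor.

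For all cohorts except GBM/AA, Section 8.1 says to stop study treatment at confirmed progression (iCPD). A note allows for participants with meaningful benefit: "an exception to continue treatment and tumor assessments until clinical disease progression may be considered following consultation with the sponsor". Section 10.6.2 repeats this: "an exception to continue study treatment may be considered following consultation with the Sponsor". The iCPD row of Table 10-4 says the same for clinically stable participants.

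For GBM/AA, Section 8.1 says "If PD occurs beyond 6 months after initiation of treatment, the participant should be discontinued from treatment". It also says to stop when the investigator judges PD to be true progression rather than pseudoprogression. Neither sentence has an exception. Section 10.6.4 describes stopping for worsening beyond 6 months as a recommendation.

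On consent, Section 6 says "Re-consent also covers a potential treatment continuation with regorafenib after confirmed radiological progression". Section 10.1.3 says the same and adds that this runs until clinical progression.

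**The concern.** A stopping rule should give one answer for one patient. Here a site that continues treatment after confirmed progression on the physician's judgment follows Section 7.1, yet has not met the condition in Sections 8.1 and 10.6.2. In GBM/AA the same decision is permitted by one section and has no stated route in another.

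The stakes are patient safety, the scope of what participants were asked to agree to, the exposure that is reported, and whether a given continuation counts as a protocol deviation.

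**Working it through.** No arithmetic applies: no error rate, response rate, sample size or event count enters. The check sets the statements side by side on three questions and then looks at the endpoints.

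**1. Must the sponsor be consulted (iRECIST cohorts)?**

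| Place | At confirmed PD | Exception | Sponsor step |
|---|---|---|---|
| 7.1 | Withdraw both drugs | Treating physician judges ongoing benefit | None stated |
| 8.1 | Discontinue | Clinically meaningful benefit | Consultation |
| 10.6.2, text | Discontinue | Clinically meaningful benefit | Consultation |
| Table 10-4, iCPD row | Discontinue | Possible | Consultation |

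One place has no sponsor step and three require it. Take a participant with iCPD whose physician sees benefit and continues treatment without contacting the sponsor: Section 7.1 is satisfied and the other three are not.

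The silence in Section 7.1 is hard to read as an implied sponsor step, because that section names such steps elsewhere. Continuing regorafenib after an interruption of more than 28 days requires sponsor consultation, and some nivolumab delays beyond 10 weeks require Medical Monitor approval. Cross-references do not settle the matter: Section 6 sends the reader to 7.1 for discontinuation criteria and to 8.1 for treatment beyond progression.

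The difference matters for deviations. Section 8 forbids waivers but exempts pre-specified exceptions that call for discussion with the sponsor. A continuation without that discussion falls outside this exemption if 8.1 governs, and is simply allowed if 7.1 governs.

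**2. Is there an exception for GBM/AA?**

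- Section 7.1: yes, after PD confirmed by iRANO, on the treating physician's judgment.
- Section 8.1: none, at PD beyond 6 months or at PD judged to be true progression. The sponsor-consultation note is written for iCPD and so does not reach this cohort.
- Section 10.6.4: stopping beyond 6 months is recommended.

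These are three different strengths for one decision. The triggers also differ: 7.1 speaks of confirmed PD, while the 6-month sentence in 8.1 speaks of PD without asking for confirmation. The clearest overlap is PD judged to be true progression, where 8.1 says stop and 7.1 allows continuation.

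**3. Which drug does the described re-consent cover?**

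- Sections 7.1, 8.1 and 10.6.2 refer to treatment or study treatment without limiting the drug.
- Sections 6 and 10.1.3 name regorafenib only for the period after confirmed progression. The re-consent needed after initial RECIST 1.1 or RANO progression is described without a drug limit.

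A participant with fewer than 24 infusions could therefore receive nivolumab after confirmed progression under the treatment rules, while the consent description for that period does not mention it.

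**4. Which outputs are touched?**

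ORR uses RECIST 1.1 or RANO, and Section 8.1 ends those assessments at progression. Section 9.4.3 ends DOR and PFS at first documented progression or death. First progression comes no later than its confirmation, so dosing after confirmation cannot change these endpoints. Treatment duration, reported under SAP Section 5.6.1, does lengthen with continuation, and protocol deviations are reported under SAP Section 6.4.

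**The case against.** The best defence is that the passages can be read together. Section 7.1 says who judges benefit; it does not say that the physician acts alone. Sections 8.1 and 10.6.2 ask for consultation, not approval, so the sponsor is not made the decider. A site that follows 8.1 also satisfies 7.1, and Sections 4.1.2 and 6 both point to 8.1 for detail. This is fair as far as it goes: the disagreement is about whether the sponsor must be involved, not about who has the final word. But compliance runs one way only, since a site that follows 7.1 as written does not satisfy 8.1. The joint reading also gives no help in GBM/AA, where 8.1 has no exception to join to.

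For GBM/AA one can add that 8.1 uses should, that 10.6.4 only recommends, and that the triggers are not identical. This softens the contradiction but does not remove it.

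Three stronger readings are tempting, and the documents do not support them:

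- A reader might infer that the treatment rules conflict on which drug may continue. No treatment rule limits continuation to regorafenib; the mismatch lies only in the consent description.
- A reader might infer that nivolumab after confirmed progression would be given without consent. The re-consent sentences are worded inclusively, and the consent form is a separate document that is not available here.
- A reader might infer that AE collection windows or OS would differ by site. The AE window is a fixed rule: 30 days (+7) after treatment discontinuation or 100 days (+14) after the last nivolumab dose, whichever is later. Longer treatment only moves its start. Nothing in the documents supports an effect on OS.

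**Conclusion.** The point holds as a contradiction within a stopping rule. Section 7.1 omits the sponsor consultation that three other places require for the iRECIST cohorts, and it gives GBM/AA an exception that Section 8.1 does not. The re-consent description is a separate and lesser mismatch of scope.

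It bears on participants with confirmed progression whose physician sees continuing benefit. Their number cannot be derived from the documents, and the clinical-stability and re-consent conditions for treating beyond first progression narrow the group. For the statistical analysis the matter is minor, because the primary endpoint and the progression-based secondary endpoints do not depend on it.

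The conclusion rests on the text of protocol amendment 1 and SAP version 3.0. SAP version 2.0, to which version 3.0 defers for deviations and exposure, and the consent forms were not available.

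**What to change.** Reconcile protocol Sections 6, 7.1, 8.1, 10.1.3, 10.6.2 (with Table 10-4) and 10.6.4 so that they agree on:

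- whether sponsor consultation is required before treatment continues after confirmed progression;
- whether any exception applies to GBM/AA, and at which trigger;
- which drug or drugs the re-consent covers after confirmed progression.

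State also which rule governs the classification of protocol deviations. Which clinical rule is right is for the sponsor and investigators to settle, and none is proposed here.

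The cost is wording alignment in the protocol and, if needed, the re-consent form. SAP version 3.0 is written for the point when all participants had left the trial, so at that stage new wording cannot change conduct. What remains useful then is a short statement in the report of the rule used to classify deviations, and of whether consent covered any nivolumab given after confirmed progression.
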